9.5.2.2 Bone Safety Analysis

The incidence of orthopedic complications (i.e. with focus on bone non-union as per X-ray imaging) will be summarized through frequency counts by treatment group. The treatment contrasts will be presented as odds ratios and/or absolute risk differences with corresponding 2-sided 95% confidence intervals depending on the rarity of the event.

9.5.2.3 Adverse events

Treatment emergent adverse events (events start after the first dose of investigational treatment or events present to the first dose of investigational treatment but increased in severity) will be summarized by primary system organ class, preferred term and treatment.

Incidence of potential cases of safety risks as defined in the case retrieval strategy with frequency counts by treatment arm and estimated rates with corresponding 95% confidence intervals regardless of investigational treatment relationship will be provided to compare each of bimagrumab treatments with placebo group.

Separate summaries will be performed for study medication related events, death, serious adverse events, adverse events leading to discontinuation of the investigational study drug , and other adverse events of interest.

Additional analyses utilizing the beta binomial model may be used to summarizing absolute rates by treatment group in the case of sparse data or if it is clinically warranted. The beta binomial model will utilize a non-informative beta (1/3, 1/3) prior. Summaries may include posterior probabilities for a clinically relevant difference(s), point estimates under the posterior distribution with corresponding 95% credible intervals (i.e., equal tail) and/or a graphical presentation of the entire posterior distribution itself.

9.5.2.4 Laboratory data

The summary of laboratory measurements by visit will be presented with descriptive statistics (mean, standard deviation, minimum, median, and maximum) for quantitative variables; and with frequency for categorical variables. In addition, change from baseline will be summarized for all parameters to compare post-baseline measurements with corresponding baseline values.

Baseline values will be defined as last non-missing assessment prior to the first dose of study medication. Patients with abnormal laboratory values will be listed and selected parameters will be flagged during study conduct according to pre-defined clinically relevant values. Incidence of abnormalities based on clinically notable criteria will be tabulated.

Newly occurring or worsening liver as well as pancreatic enzyme abnormalities will be summarized.

In addition, all laboratory data will be listed by treatment, patient, and visit and if ranges are available abnormalities will be flagged.

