4.2 Exclusion criteria

Patients fulfilling **any** of the following criteria are not eligible for inclusion in this study. No additional exclusions may be applied by the investigator, in order to ensure that the study population will be representative of all eligible patients.

Central laboratory tests needed for eligibility assessment, i.e. GFR, AST, ALT, bilirubin, platelet count, hemoglobin, or ECG interpretations which fall outside of the **protocol-specified range** at screening can be repeated at an unscheduled visit during the screening epoch to confirm patient eligibility prior to randomization.

1. History of any other lower limb fracture in the past 6 months or any other major surgery to the lower limb in the past 3 months prior to randomization that caused a persisting functional sequelae, which directly impacts gait speed and/or gait quality and is unlikely to recover during the study period ;
2. Isolated high-energy sub-trochanteric fracture (AO Classification 32 A-C, ([AO Foundation 2013](#)));
3. Major mobility limitation (i.e. not able to walk 100 meters without stopping or getting help; unilateral help being fine) in the past 3 months prior to the hip fracture due to severe dyspnea, presence of permanent or progressive neurologic deficit (muscle weakness, spasticity, rigor or balance impairment), disabling joint or muscle pain in the hip or knee, intermittent claudication or major visual impairment.
4. Active gastrointestinal diseases/conditions known to cause malabsorption or increased enteric loss of protein, such as inflammatory bowel disease (unless complete remission), celiac disease (unless gluten-free diet), short bowel syndrome, pancreatic insufficiency (unless under good control by medication/enzyme supplements);
5. Severe renal insufficiency defined by either requiring dialysis or having an estimated glomerular filtration rate (GFR) < 30 mL/min using the modification of diet in renal disease (MDRD) equation which can be found in the *Study Manual*;
6. Uncontrolled hypothyroidism requiring a change in the dose of hormone replacement therapy in the last 6 weeks prior to randomization; uncontrolled hyperthyroidism;
7. Underlying muscle diseases, including history of or currently active form of inflammatory myopathies (e.g., dermatomyositis, polymyositis, etc) or muscular dystrophies;

Cardiovascular conditions

[figure not shown]

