Newly occurring clinically notable criteria will be presented, where clinically notable laboratory values will be considered newly occurring if they are not present at Baseline. If assessments cannot be made at Baseline due to missing value(s), post-baseline values meeting the clinically notable criterion will be considered as newly occurring.

The incidence of patients per laboratory test with at least one newly occurring clinically notable test result on treatment at last infusion of study drug (expected per protocol at Week 20 + 56-days) will be presented by treatment group and across active bimagrumab treatment groups combined (“Active Total: Safety” - Includes bimagrumab 700 mg, bimagrumab 210

mg and bimagrumab 70 mg), overall only. The percentage (%) per laboratory test will be calculated as the number (n) of patients with at least one scheduled or unscheduled newly occurring clinically notable test result occurring after the start of the first infusion of study drug up to and including the last available assessment assigned to treatment relative to the total number of patients “at risk” (in the SAF analysis set).

Similarly, the incidence of patients per laboratory test with at least one newly occurring clinically notable criteria result within the post-treatment follow-up will be presented by treatment group and across active bimagrumab treatment groups combined (“Active Total: Safety” - Includes bimagrumab 700 mg, bimagrumab 210 mg and bimagrumab 70 mg), overall only. The percentage (%) per laboratory test will be calculated as the number of patients with at least one scheduled or unscheduled newly occurring clinically notable criteria within post-treatment follow-up relative to the total number of patients “at risk (ongoing at the start of post-treatment follow-up).

Finally, the incidence of patients per laboratory test with at least one newly occurring clinically notable criteria result in the overall study (entire study period) will also be presented in a similar manner, as described for treatment-emergent and post-treatment follow-up.

Abnormal liver enzyme laboratory values

Abnormal liver function tests such as aspartate aminotransferase (AST), alanine aminotransferase (ALT), alkaline phosphatase (ALP) or total bilirubin (except if accompanying Gilbert’s Disease) are detailed in [Section 3.9](#) (Liver event and laboratory trigger definitions).

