The incidence of patients per abnormal liver enzyme laboratory test (ALT, AST, ALP and total bilirubin) with at least one newly occurring clinically notable criteria on treatment (at last infusion of study drug expected per protocol at Week 20 + 56-days) will be presented by treatment group and across active bimagrumab treatment groups combined (“Active Total: Safety” - Includes bimagrumab 700 mg, bimagrumab 210 mg and bimagrumab 70 mg), overall only. The percentage (%) per laboratory test will be calculated as the number (n) of patients with at least one scheduled or unscheduled newly occurring clinically notable criteria result occurring after the start of the first infusion of study drug up to and including the last available assessment assigned to treatment relative to the total number of patients “at risk” (in the SAF analysis set). The incidences in the post-treatment follow-up and overall study will be presented in a similar manner, adjusting accordingly.

Liver safety guidance analyses

The following mandatory table and by-patient data listing as required by the latest version of the Liver safety guidance (Version 2.5) will be included in RAP Module 7 (CSR Deliverables):

- Peak post-baseline: Change from Baseline to the highest post-baseline laboratory result by liver function test: ALT, AST, ALP and total bilirubin (see Table 6.2 of Liver safety guidance).
- By-patient data listing of laboratory values of patients with liver events (Listing 6.6 of Liver safety guidance).

In addition, figures will be presented. These will include:

- Box-and-whisker plots (by treatment group and across active bimagrumab treatment groups combined [“Active Total: Safety” - Includes bimagrumab 700 mg, bimagrumab 210 mg and bimagrumab 70 mg]) of /ULN-normalized values.
- Scatter plot of peak post-baseline TBL/ULN-normalized values versus peak post-baseline AST/ULN-normalized values and ALT/ULN-normalized values (Evaluation of Drug-Induced Serious Hepatotoxicity [eDISH] plots) to identify potential Hy’s Law cases.

For further details see [Section 3.2](#) (Graphical displays at the study level) of the latest liver safety guidance (Version 2.5).

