3.8 Clinically notable values

Clinically notable criteria will be used to identify notable abnormalities of key laboratory tests, vital signs values and ECG intervals.

Table 3.6 Clinically notable laboratory values, vital signs, ECG intervals and echocardiography

Laboratory Assessments	
Hemoglobin	< 8.0 g/dL
Hemoglobin	< LLN
Glycated hemoglobin (HbA1C)	≥ 7.5%
Average blood glucose (based on fasting values only)	≥ 9.0 mmol/L
Platelet count	< 75 x 10 ⁹ /L
Estimated GFR*	< 30 mL/min
Total bilirubin concentration	> 1.5 x ULN
Total serum bilirubin	> 1.6 mg/dL (27 µmol/L)
ALT	> 3 x ULN (see Table 3.7 [Liver event and laboratory trigger definitions] for more clinically notable values)
AST	> 3 x ULN (see Table 3.7 [Liver event and laboratory trigger definitions] for more clinically notable values)
ALP	> 3 x ULN (see Table 3.7 [Liver event and laboratory trigger definitions] for more clinically notable values)
Total CK	> 3 x ULN
Sodium (Na)	> ULN < LLN
Testosterone, male patients	> ULN
Testosterone, female patients	> ULN
Albumin	< LLN
Pre-albumin	< LLN
Magnesium	< LLN
BUN	< LLN
Uric acid	< LLN
Lipase	> 2 x ULN
Amylase	> 2 x ULN

Lipase	≥ 3 x ULN	
Amylase	≥ 3 x ULN	
Lipase and/or amylase	≥ 3 x ULN	
Vital Signs		
	Low	High
Systolic blood pressure (mmHg)	< 90 mmHg or decrease from Baseline of ≥ 20 mmHg	> 150 mmHg, > 180 mmHg, or increase from Baseline of ≥ 20 mmHg
Diastolic blood pressure (mmHg)	< 50 mmHg or decrease from Baseline of ≥ 15 mmHg	> 90 mmHg, > 100 mmHg, or increase from Baseline of ≥ 15 mmHg
Pulse rate (bpm)	< 60 bpm or decrease from Baseline of ≥ 15 bpm	> 100 bpm or increase from Baseline of ≥ 15 bpm
Weight (kg)	≥ 5% decrease from Baseline	
ECG		
QTcF**	≥ 450 msec for males ≥ 460 msec for females ≥ 500 msec	
QTc	> 30 msec change from Baseline or > 60 msec change from Baseline	
PR	> 250 msec	
ECHO		
	Low	High
Left ventricular ejection fraction (%)	- ≥15% decrease in ejection fraction from Baseline - Decrease in ejection fraction to a value less than 45%	
Interventricular septum thickness(mm), measured at end-diastole		- > 15mm septum thickness - ≥ 50% increase in thickness from Baseline
Left ventricular posterior wall thickness (mm)		- > 15mm wall thickness - ≥ 50% increase in thickness from Baseline

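### The SAP drops the worsening half of the protocol's pancreatic enzyme summary, so patients already at or above 3 x ULN at Baseline, and rises that cross no tier, enter no incidence count

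*Protocol*

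**What the plan says.** Protocol 9.5.2.4 makes two commitments. The specific one is: "Newly occurring or worsening liver as well as pancreatic enzyme abnormalities will be summarized". The general one is to tabulate the incidence of abnormalities against the clinically notable criteria, with no condition on the Baseline value.

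SAP 2.11.7 sets the counting rule: "clinically notable laboratory values will be considered newly occurring if they are not present at Baseline". If Baseline is missing, "post-baseline values meeting the clinically notable criterion will be considered as newly occurring". The on-treatment table is described as "The incidence of patients per laboratory test with at least one newly occurring clinically notable test result on treatment". The follow-up and whole-study tables use the same rule.

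The thresholds are in SAP 3.8, Table 3.6. The lower tier is "Lipase > 2 x ULN", and amylase has the same. The upper tier is 3 x ULN, given for each enzyme separately and as a combined row, "Lipase and/or amylase ≥ 3 x ULN". There is no higher tier.

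For the liver tests only, SAP 2.11.7 adds a table of values above cut-offs that does not depend on Baseline, and a peak table: "Change from Baseline to the highest post-baseline laboratory result by liver function test: ALT, AST, ALP and total bilirubin".

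SAP 2.14, which lists departures from the protocol, does not mention worsening.

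**The concern.** The SAP history says it was revised for Amendment 4, and SAP section 1 says the analysis follows section 9 of that amendment, so an outdated protocol version does not explain the gap. Amendment 4 added the lipase and amylase monitoring. Protocol 3.6 describes the elevations as dose-dependent and reports two confirmed cases of acute pancreatitis in the programme. Protocol 7.4 aims to determine the potential for pancreatic events.

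Raised values at entry are possible. Lipase and amylase are measured at Screening (protocol Table 6-3), but they are not among the "Central laboratory tests needed for eligibility assessment, i.e. GFR, AST, ALT, bilirubin, platelet count, hemoglobin" listed in protocol 4.2. If a patient already above the top tier rises further on drug, the table meant to show pancreatic abnormality by dose cannot register it. At stake is whether the report delivers the promised summary for a safety finding under active evaluation.

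**Working it through.** The plan gives no figure to reproduce. The check applies the SAP rule to illustrative values.

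**Rule.** For a criterion C, a patient is counted if C is met after Baseline and not met at Baseline. The criteria are > 2 x ULN and >= 3 x ULN (Table 3.6). The SAP words the table per laboratory test, so two readings were tried:

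- A: each Table 3.6 row is its own criterion.
- B: any notable value at Baseline blocks all later counting for that test.

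The shift table in SAP 2.11.7 has a single High class above ULN.

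| Baseline (x ULN) | Later value (x ULN) | Counted under A | Counted under B | Shift |
|---|---|---|---|---|
| 0.8 | 3.5 | > 2 and >= 3 | > 2 and >= 3 | Normal to High |
| 1.5 | 1.9 | none | none | High to High |
| 1.5 | 2.5 | > 2 | > 2 | High to High |
| 1.5 | 3.5 | > 2 and >= 3 | > 2 and >= 3 | High to High |
| 2.5 | 2.9 | none | none | High to High |
| 2.5 | 3.5 | >= 3 | none | High to High |
| 2.5 | 6 | >= 3 | none | High to High |
| 3.2 | 8 | none | none | High to High |

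**Result.**

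- Entry above ULN but not above 2 x, then crossing a tier: counted under both readings.
- Entry above 2 x and below 3 x, then reaching 3 x: counted only under A. A is the natural reading, and the missing-Baseline rule, which refers to the criterion, supports it. The text does not settle the matter.
- Entry at or above 3 x: not counted for that enzyme under either reading, however far the value rises.
- A rise that crosses no tier: not counted under either reading.

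**Other outputs for the uncounted patients.**

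- Change-from-Baseline summaries and mean-change plots are at group level.
- Minimum and maximum are suppressed at the primary analysis (SAP 2.4.1 and 3.2), so an extreme value does not show there.
- By-patient listings show the values but give no count by arm.
- The adverse-event-of-special-interest searches in SAP 2.11.6 include no pancreatic category.
- The cut-off and peak tables cover ALT, AST, ALP and bilirubin only.

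**Size per patient.** The planned arms are 70, 70, 70 and 35. One uncounted patient is 1/70 = 1.4 percentage points in a 70-patient arm and 1/35 = 2.9 points in the 70 mg arm. In the pooled active column (70 + 70 + 35 = 175) it is 1/175 = 0.6 points. The documents give no Baseline distribution of lipase or amylase, so these figures cannot be turned into an expected shortfall.

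**The case against.** The strongest reply is that the rule is defensible and its consequence small. Incidence of newly occurring abnormality is a legitimate quantity. Baseline elevation precedes treatment, the arms are randomized, and the rule applies alike in each. Few patients may enter at or above 3 x ULN: exclusion 18 removes acute or chronic pancreatitis, and exclusion 26 lets the investigator exclude for a laboratory finding that adds risk. A patient who does worsen is not invisible. Protocol 7.4 calls for re-check, symptom assessment and imaging at 3 x ULN or more whatever the Baseline. Clinically significant values are adverse events, and treatment-emergent events include worsening. The table shells (RAP Module 7) are outside the documents and might say more.

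Most of this stands as a limit on the consequence. It does not remove the mismatch: the protocol promised newly occurring or worsening, the SAP defines only the first, and the change is not declared. Adverse-event capture depends on investigator judgement and does not replace a tabulation of laboratory values.

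Two stronger readings are tempting, and the documents support neither. A reader might infer that anyone with raised lipase or amylase at entry who worsens goes uncounted. The check contradicts this, because the rule works against the two tiers and not against ULN. A reader might also infer that incidence by dose is understated. No Baseline frequency is given, no distortion of the comparison between arms is demonstrated, and the missing-Baseline rule pushes the count the other way.

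**Conclusion.** The point holds in a limited form. The SAP does not deliver the worsening part of the protocol's pancreatic enzyme summary and does not say so. The firm gap is patients at or above 3 x ULN at Baseline, together with rises from a raised Baseline that cross no tier. Patients entering between 2 x and 3 x ULN fall into it as well only if the per-test wording is read strictly.

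The number affected is unknown and may be small. Incidence may be understated, at 1.4 percentage points per uncounted patient in a 70-patient arm, but that is a possibility and not a finding. The conclusion rests on the SAP text as written and assumes that no unseen table specification adds a worsening count.

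**What to change.** In SAP 2.11.7:

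1. Add for lipase and amylase a by-arm count of patients whose highest post-baseline value falls in a higher ULN-multiple category than Baseline. Include at least one category above 3 x ULN. The exact bands are the sponsor's choice. For example, any cut above 3.2 and up to 8 x ULN would register the 3.2 to 8 case. Label the table as newly occurring or worsening, to match protocol 9.5.2.4.
2. State that each row of Table 3.6 is a separate criterion, which settles the 2 x to 3 x ULN group.
3. Extend the peak post-baseline change table to lipase and amylase. Rises within a band will still not be counted under item 1, and this table shows their size.

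If the sponsor prefers to count new occurrences only, the least it should do is record that departure in SAP 2.14, although this leaves the summary undelivered.

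The cost is a small amount of table programming. The peak table exists for the liver tests and can be extended, but the SAP describes no table that counts moves to a higher category, so that one is new. No new samples or visits are needed.

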9.5.2.5 ECG

Summary statistics will be presented for ECG variables by visit and treatment group utilizing Novartis standard algorithms and reporting formats. All ECG data will be listed by treatment, patient and visit, abnormalities will be flagged.

9.5.2.6 Echocardiography

Summary statistics will be presented by visit and treatment group for the following measurements:

[figure not shown]
- Left ventricular wall (posterior) and septal thickness

- Left ventricular mass and mass index
- End-diastolic volume
- End-systolic volume
- Left ventricular ejection fraction
- Left ventricular diastolic and systolic diameter
- Left atrial size and volume
- Right ventricular wall thickness and dimension

All echocardiographic data will be listed by treatment, patient and visit.

[figure not shown]
[figure not shown]
9.5.2.7 Vital signs

[figure not shown]
[figure not shown]
Summary statistics for vital sign variables and for the change from baseline in vital signs will be presented. Abnormalities according to clinically notable criteria will be identified and the incidence of abnormalities will be tabulated. All vital signs data will be listed by treatment, patient, and visit and if ranges are available abnormalities (and relevant orthostatic changes) will be flagged.

9.5.2.9 Other safety variables

[figure not shown]
Other safety variables will be summarized by visit and treatment group and will be listed by treatment, patient, and visit. Other safety variables include death, pain scores for AEs of spontaneous muscle contraction, [redacted]

9.6 Interim analyses

The primary analysis will be performed when all patients have completed their EoT visit (Week 24) via an interim database lock (soft database lock); while an updated analysis will be conducted when all patients have completed their EoS visit (Week 48). No interim analysis will be performed prior to the primary analysis at the Week 24 EoT visit.

9.7 Sample size and power calculation

A total sample size of approximately 245 patients at the time of randomization is planned (calculated using NQuery 7.0). Specifically, there will be 70 patients randomized to the placebo, bimagrumab 210 mg, and bimagrumab 700 mg groups for hypothesis testing purposes. An additional 35 patients will be randomized to the bimagrumab 70 mg group for the purpose of conducting formal dose response modeling described in the supportive analysis (section 9.4.4), but not for hypothesis testing. .

Total lean body mass

The primary objective of the study is to demonstrate that bimagrumab induces increases in Total LBM (change from baseline) compared to placebo at Week 24. A meaningful difference in LBM (change from baseline) increase has been identified as being 1.0 kg over placebo.

Study BYM338X2102 cohort 1&2 data showed that at Week 12, 5 subjects in 10 mg/kg bimagrumab group had LBM change from baseline mean = 1.48 kg (std = 0.86 kg); 6 subjects in 3 mg/kg bimagrumab group had LBM change from baseline mean = 2.22 kg (std = 1.13 kg).

Assuming that at Week 24 total LBM (change from baseline) difference between bimagrumab and placebo will be 1.0 kg and common SD = 1.0 kg, then sample size of 70 per group will show the power of 99%. Table 9-1 shows the power of detecting a significant difference between bimagrumab and placebo in LBM at Week 24 by two-sided test at alpha level = 0.025 (adjusted for 2 comparisons).

Table 9-1 Power calculation for total LBM (sample size = 70 per arm)

Common SD [kg]	Total LBM difference (bimagrumab – Placebo) [kg]				
	0.8	0.9	1.0	1.1	1.2
1.0	99	99	99	99	99
1.2	95	98	99	99	99
1.4	86	93	97	99	99
1.6	75	85	92	96	98

Gait Speed

One of the secondary objectives is to characterize for each bimagrumab treated group the placebo-corrected change in gait speed (GS) from baseline to Week 24. A treatment effect of 0.1-0.2 m/s between bimagrumab and Placebo has been deemed to be a clinically meaningful difference (Alley et al 2011).

The references in Table 9-2 were consulted in order to understand the variability and magnitude of treatment effect to be anticipated in 6 months on 4 m gait speed.

[figure not shown]

Table 9-2 Key references used to ascertain the variability in gait speed

Reference	Study Design	Population	Information
Latham et al (2008)	Randomized, double-blinded, placebo-controlled trial	Patients >65 years undergoing surgical repair of a hip fracture	Gait speed at baseline 0.50 (0.28) m/sec. Gait speed at Week 12 0.77 (0.35) m/sec
Alley et al (2011)	Prospective study patients presenting for hip fracture repair	217 women > 65 y able to walk before hip fracture.	Gait speed at month 2 0.36 (0.17) m/Sec. Gait speed month 12 0.52 (0.24) m/Sec Standard deviation of gait speed change score ranging from 0.19 to 0.25 m/sec (*) in an analysis stratified for self-reported improvement perception outcome
Hardy et al (2007)	Prospective cohort study without intervention	439 community dwelling adults > 65 y. No use of assisted devices. Gait speed between 0.2 m/sec and 1.2 m/sec	Baseline Gait speed 0.88 (0.24) m/sec 1 year Gait speed 0.91 (0.29) m/sec Change scores 0.03 (0.19) m/sec

Based on the references above, in particular [Latham et al \(2008\)](#), it is anticipated that the difference from baseline in gait speed will have a standard deviation between 0.2 and 0.3 m/Sec.

Assuming that at Week 24 gait speed (change from baseline) difference between bimagrumab and placebo will be 0.15 m/sec and common SD = 0.25 m/sec, then sample size of 70 per group will give a power of 94% using a two-sided test at alpha level = 0.05 (based on testing strategy). The assumed standard deviation of 0.25 is the best available estimate given the literature review.

Short physical performance battery (SPPB)

The other secondary objective is to demonstrate that bimagrumab induces increases in SPPB (change from baseline) compared to placebo at Week 24. [Perera et al \(2006\)](#) estimated that, the meaningful change using effect size analysis, SPPB score changes corresponding to small and moderate effect sizes were 0.54 and 1.34 points respectively. Hence a meaningful difference in SPPB (change from baseline) increase has been identified as being 1.0 point over placebo.

The references in [Table 9-3](#) were consulted in order to understand the variability and magnitude of treatment effect to be anticipated on SPPB in 6 months. Common standard deviation for change from baseline at month 6 in SPPB have been estimated based on 95% confidence interval for the changes from baseline in SPPB from [Latham et al \(2014\)](#). When assuming respective group sample sizes of 95 and 100 and using a multiple imputation technique to address missing data, SD is estimated to 1.5. When assuming respective group sample sizes of 95 and 100 and using a multiple imputation technique to address missing data, SD is estimated to 1.4.

Table 9-3 Key references used to ascertain the variability in SPPB

Reference	Study Design	Population	Information
Latham et al (2008)	Randomized, double-blinded, placebo-controlled trial	Patients >65 years undergoing surgical repair of a hip fracture	SPPB at baseline 4.7 (2.8) SPPB at Week 12 7.9 (2.6)
Latham et al 2014	Randomized, double-blinded, placebo-controlled trial	232 functionally limited older (78-79 years) adults who had completed traditional rehabilitation after a hip fracture	SPPB at baseline 5.9 (2.8). SPPB at Week 24 6.2 (3.0) and 7.2 (3.0) in the placebo and exercise intervention groups, respectively Changes in SPPB from baseline at Month 6 was 0.2 (95% CI 0-0.5) in the control and 1.0 (95% CI 0.8-1.3) in the exercise group
Adunsky et al 2012	Randomized, double-blinded, placebo-controlled trial	123 patients 60+ years old with maximum 4 days after a non-complicated surgical hip fracture repair	SPPB at baseline was 9.1 (2.2) in the treated and 8.9 (2.6) in the placebo group, respectively Changes in SPPB from baseline were 4.5 (2.2) and 3.3 (2.7), respectively

Assuming that at Week 24 SPPB (change from baseline) difference between bimagrumab and placebo will be 1.0 point and common SD = 1.5 point, then sample size of 70 per group will give the power of 97% using a two-sided test at alpha level = 0.05 (based on testing strategy).

Falls

A secondary objective of the study is to evaluate the effects of bimagrumab vs. placebo on the incidence of falls when the primary analysis is conducted. The analysis conducted for falls will include all available information collected in patients including information from visits after Week 24. Patients randomized to the active doses of 700mg and 210mg will be combined and compared to placebo, with the assumption that the differences in the incidences of fall within the bimagrumab doses (700 mg and 210mg) are minimal than the differences with the placebo arm. The annualized placebo fall rate is considered as 30% and a clinically meaningful ratio in the fall rate of the active doses relative to placebo is considered as 0.7 ([Gillespie et. al. \(2012\)](#)).

[Table 9-4](#) shows the power of detecting a significant difference between the active doses of bimagrumab and placebo in falls at Week 24, assuming sample sizes of 140 and 70 patients, respectively, negative binomial rates ([Zhu and Lakkis 2014](#)) with over dispersion parameter $k=1$ and using a two-sided test at alpha level = 0.05. It is also assumed that the average follow-up per patients will be 9 months.

[figure not shown]

Table 9-4 Power calculation for falls (sample size: BYM combined (210mg and 700mg) arm=140 and Placebo= 70)

Active bimagrumab annual fall rate	Placebo annual fall rate	Rate Ratio	Power, %
0.21	0.30	0.7	16.3
0.15	0.30	0.50	42.9
0.10	0.30	0.33	72.7
0.28	0.40	0.7	19.5
0.20	0.40	0.50	52.0

If the background placebo rate for the incidence of fall is 30% and if the rate reduction for the combined bimagrumab arm is 30% then the study will have less than 20% power. However, if the rate reduction is 67% (assuming the background placebo rate as 30%) then the study will have approximately 73% power.

10 Ethical considerations

[figure not shown]
